STUDY OBJECTIVE(S)	
Primary objective
 
Evaluate long term skeletal response to eliglustat in adult patients who successfully completed one of the Phase 2 or Phase 3 eliglustat studies.
 
Secondary objective(s)
 
Evaluate the safety of eliglustat (by (serious) adverse event (AE) continuous monitoring), the quality of life (Short Form-36 Health Survey (SF-36)) and biomarkers of Gaucher disease type 1 (GD1) (chitotriosidase, plasma glucosylceramide (GL-1) and lyso glucosylceramide (lyso-GL-1)) in adult patients who successfully completed one of the Phase 2 or Phase 3 studies.

STUDY DESIGN	
This is an open label, interventional, non-comparative, multicenter, multinational Phase 3b study to evaluate long term skeletal response to eliglustat and eliglustat safety and effect on quality of life in adult patients who successfully completed one of the Phase 2 or Phase 3 studies in the eliglustat program. This study is considered an extension of these previous studies and will continue to evaluate the safety of eliglustat and patients' quality of life (SF-36).
 
Participating investigators will enroll patients who successfully completed one of the Phase 2 or Phase 3 studies. Patients will be treated for a minimum of 2 years and up to 4 years, or until eliglustat is approved and available to patients through reimbursement. If after 4 years since the beginning of the study eliglustat is not approved and available to patients in participating country, patients in this country may continue to receive study treatment until eliglustat is available to patients through the compassionate use (expanded access) program or is approved and available through reimbursement, whichever comes first.

STUDY POPULATION Main selection criteria	
Adult patients who completed successfully the Phase 2 (GZGD00304) or a Phase 3 study (GZGD02507, GZGD02607 or GZGD03109).
 
Inclusion criteria
 
I 01. The patient must have successfully* completed the Phase 2 (GZGD00304) or a Phase 3 study (GZGD02507, GZGD02607 or GZGD03109).
 
* Successful completion is defined as patients enrolled in one of the above mentioned studies who received eliglustat through the end of the study and completed the end of study visit without having

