In the Pivotal Phase 3 Study GZGD02507 where patients were randomized to eliglustat or placebo, the total bone marrow infiltration score, as assessed by MRI in lumbar spine and femur, decreased by a mean of 1.1 point after 9 months (n = 20) and 2.15 points after 18 months (n = 18) in the eliglustat group. The percentage of eliglustat treated patients with a clinically significant reduction of at least 2 points in the total bone marrow infiltration score increased from 26% (n = 5) after 9 months to 44% (n = 8) after 18 months. After 18 months of eliglustat treatment the mean (SD) lumbar spine BMD T score increased from -1.06 (0.82) (n = 17), within the osteopenic range, to -0.91 (0.88) (n = 15), within the normal range. Statistically significant reductions in plasma MIP-1 β , which is considered to be a biomarker of active bone disease, were observed with eliglustat compared with placebo (least squares [LS] mean treatment difference = -43.5%, p<0.0001). After 18 months and 30 months of treatment, BMB score had decreased by a mean of 2.2 points (n=18) and 2.7 (n=15) points, respectively, for the patients originally randomized to eliglustat, compared to a mean decrease of 1 point (n=20) and 0.8 (n=16) in those originally randomized to placebo, and the percentage of eliglustat-treated patients with a significant reduction of at least 2 points in the total BMB score increased to 44% (n=8). After 18 and 30 months of treatment with eliglustat in an open-label extension phase, the mean lumbar spine Z-score in all patients increased from -1.208 (1.0546) at Baseline (n=38) to -0.949 (1.1447) (n=31). After 30 months and 4.5 years, the Z score further increased to -0.761 (1.0760) (n=31) and -0.478 (0.7870) (n=9), respectively (GZGD02507: 39-week [primary analysis period] and 78-week clinical study reports).

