## 1 OVERVIEW AND INVESTIGATIONAL PLAN

### 1.1 STUDY DESIGN AND RANDOMIZATION

This is an open label, interventional, non-comparative, multicenter, multinational Phase 3b study to evaluate long term skeletal response to eliglustat and eliglustat safety and effect on quality of life in adult patients who successfully completed one of the Phase 2 (GZGD00304) or Phase 3 studies (GZGD02507, GZGD02607, GZGD03109) in the eliglustat program. This study is considered an extension of these previous studies and will continue to evaluate the safety of eliglustat and patients' quality of life (SF-36).

Participating investigators will enroll patients who successfully completed one of the Phase 2 or Phase 3 studies. Patients will be treated for a minimum of 2 years and up to 4 years, or until eliglustat is approved and available to patients through reimbursement. If after 4 years since the beginning of the study eliglustat is not approved and available to patients in participating country, patients in this country may continue to receive study treatment until eliglustat is available to patients through the compassionate use (expanded access) program or is approved and available through reimbursement, whichever comes first.

Note: Eliglustat (United States Adopted Name [USAN]: eliglustat tartrate, previously Genz-112638) is an L-tartaric acid salt, and exists in plasma as a free base, Genz-99067, which is the active moiety. Throughout this SAP, Genz-99067 is used when referring to drug exposure (eg, plasma concentrations), and eliglustat is used in all other instances.

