#### **2.4.4 Analyses of efficacy endpoints**

In reference to the study period, efficacy result will be evaluated for all patients at the 2 year point by measured values (eg, category of bone pain, or bone density value in g/cm^2) and changes from baseline (eg, shift in category of bone pain or absolute and percent change from baseline in BMD g/cm^2 or incidence over 2 years, as appropriate).

In reference to the period of eliglustat treatment, efficacy result will be evaluated 2 years after study entry, but results will be grouped by duration of eliglustat treatment at the time of analysis. The actual groupings will depend on the distribution of treatment duration at the time of analysis (eg,  $\leq 5$  years versus  $>5$  years).

When the study has completed, summaries will be performed comparing to the 2 baselines as described above if applicable.

All efficacy endpoints will be summarized descriptively; no hypothesis testing will be performed. In general, descriptive statistics (number, mean, standard deviation, minimum and maximum) of the absolute value, change from baseline and/or percentage change from baseline for continuous endpoints will be analyzed. Summary statistics (count, percentage) will be summarized for the categorical endpoints. Cumulative incidence (n, percentage), incidence rate (n/year), or other descriptive statistics will also be displayed as appropriate. Calculations and summaries will include all non-missing data at a given time point, imputation will not be performed.

By-patient data listings containing efficacy endpoints will be produced if necessary.

All the below mentioned other efficacy endpoint analyses will be produced for the full analysis population. Refer to [Section 2.5.3](#) for details on handling dropouts, missing data, and patients who have more than one value assessed within the same time frame.

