#### **2.4.4.1.3 BMD**

Absolute value, change and percent change from baseline (study baseline and eliglustat baseline) for bone mineral density in (g/cm^2), T and Z scores by location will be summarized by visit. Shift in bone density categories of T and Z scores will be summarized by visit. In addition, mean plots of absolute values and percent change from baseline for total BMD, T-scores, and Z-scores for all patients with standard deviation will be provided.

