### **2.5.4 Windows for time points**

The time window is defined as below to create analysis visit. The relative day below is referred to the first dose intake in the EFC13781 study. The end of study is defined as patient completed at least 2 years of follow-up (unless early discontinuation) up to 4 years or early discontinued from the study or until commercial eliglustat is available to the patients. Thus, the analysis visit list may be longer than the list below. The same algorithm will be applied to the trailing visits after the Week 416 if applicable.

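### After Week 104 the absolute-mean BMD, T-score and Z-score plots can move because the patient set changes, and for T and Z scores the figures show no usable within-patient measure

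*SAP*

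**What the plan says.** SAP 2.4.4.1.3 first specifies tables by location and visit: "Absolute value, change and percent change from baseline (study baseline and eliglustat baseline) for bone mineral density", and likewise for T and Z scores, with shifts in density category. It then adds figures: "mean plots of absolute values and percent change from baseline for total BMD, T-scores, and Z-scores for all patients with standard deviation". So two kinds of figure are planned, absolute means and percent change. Absolute change is not among them.

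SAP 2.4.4 settles who enters each point: "Calculations and summaries will include all non-missing data at a given time point, imputation will not be performed". Neither document fixes the patient set for the figures, asks for n on them, or pairs a plotted absolute mean with the baseline mean of the same patients.

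Follow-up differs between patients. SAP 1.1 states "Patients will be treated for a minimum of 2 years and up to 4 years, or until eliglustat is approved", and the Protocol synopsis has treatment run "until eliglustat is approved and available to patients through reimbursement". Beyond four years continuation depends on country: "If after 4 years since the beginning of the study eliglustat is not approved and available to patients in participating country" (SAP 1.1). SAP 2.5.4 lists analysis visits to Week 416 and adds "The same algorithm will be applied to the trailing visits after the Week 416 if applicable".

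The Protocol synopsis allows up to 20 months for enrollment. SAP 3 bases the two-year analysis on all data collected up to the date on which every patient has completed two years.

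DXA covers both hips and the lumbar spine (Protocol 9.1.3, SAP 2.1.3.1.3). The *total BMD* named in the figure sentence is not defined.

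**The concern.** A line joining visit means invites the reader to see a course over time. If the patients behind the points differ, part of that course is composition: a visit mean rises when those who remain had better bones from the start. SD bars show the spread between patients. They do not show how many patients are left or that the set has changed.

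The study is single-arm and descriptive, so no comparator would expose such a drift, and bone density is one of the primary endpoint components. The Protocol's introduction already describes a series with a falling n as a continuing rise: "After 30 months and 4.5 years, the Z score further increased to -0.761 (1.0760) (n=31) and -0.478 (0.7870) (n=9), respectively".

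Percent change is measured within patients and would normally be the safeguard. It works for a density in g/cm², which is always positive. It does not work for a score that can be negative or close to zero.

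**Working it through.** The plan gives no figure for this point, so there is none to reproduce. The check asks how far the absolute mean could move if no patient's value changed.

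**1. Inputs from the documents.** About 32 patients at about 4 sites (Protocol synopsis). Lumbar spine Z-score SD 1.076 (n=31) and 0.787 (n=9) (Protocol 4). **Not in the documents, so assumed:** how many patients remain at each visit, who leaves first, site sizes, differences between sites, and DXA measurement error.

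**2. Random exit.** If n of 32 remain at random, the SD of the shift in the mean is SD × √(1/n − 1/32), and the 95% range is 1.96 times that.

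| Remaining | SD 0.787 | SD 1.076 |
|---|---|---|
| 16 | 0.787 × 0.177 = 0.139; ±0.27 | 1.076 × 0.177 = 0.190; ±0.37 |
| 8 | 0.787 × 0.306 = 0.241; ±0.47 | 1.076 × 0.306 = 0.329; ±0.65 |

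Protocol 4 also reports one larger SD, 1.1447 at 18 months, which would give ±0.40 and ±0.69. For scale, the rise it reports from 18 to 30 months is −0.761 − (−0.949) = 0.188.

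**3. Systematic exit.** If leavers average d lower than stayers, the mean rises by d × (number gone)/32. With d = 0.5 this is 0.5 × 16/32 = 0.25 with 16 left, and 0.5 × 24/32 = 0.375 with 8 left. For d from 0.25 to 1.0 the ranges are 0.125 to 0.50 and 0.19 to 0.75. If leavers average higher, the mean falls by the same amounts.

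**4. Staggered entry.** When the last patient reaches two years, the first may have 24 + 20 = 44 months of follow-up. Week 156 is about 36 months, so if enrollment takes the full 20 months, only patients enrolled in about the first 44 − 36 = 8 months can have reached that visit, even if nobody has left.

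**5. Percent change for T and Z scores.** Using the Phase 2 means in Protocol 4:
- T-score −1.63 to −0.88: 0.75 / (−1.63) = −46%.
- Z-score −1.17 to −0.48: 0.69 / (−1.17) = −59%.

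Both are improvements and both come out negative. These are ratios of means. The plot would average individual percentages, where a baseline near zero gives an arbitrarily large value and patients with positive and negative baselines carry opposite signs for the same improvement.

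**6. Absolute within-patient change.** With no true change, only measurement error remains. Assuming a measurement SD of 0.2, the SD of the mean change at n = 8 is √2 × 0.2/√8 = 0.10. A simulation of 20,000 trials (4 sites of 8, total SD 1.076, between-site SD 0 to 0.5) gave an SD of 0.34 to 0.53 for the shift in the absolute mean at n = 8. A spurious shift of at least 0.188 occurred in 58% to 72% of trials with the absolute mean, against about 6% with mean change.

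**The case against.** The case against has substance.

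- **A within-patient plot is already planned.** The sentence that specifies the absolute means also specifies percent change. This stands for BMD in g/cm², but step 5 shows why it does not for T and Z scores.
- **The tables already hold the answer.** Change from both baselines is tabulated by location and visit, and the summaries include the number of patients. This stands, and it limits the point to the figures.
- **The main time point is safe.** The main analysis is at two years and treatment lasts at least two years. Before Week 104 only early discontinuation or missing data can alter the set. This stands.
- **The counts of 16 and 8 are assumptions.** They are, and are labelled so.
- **Printing n is a matter for figure shells.** Fair; silence in the SAP does not show that n will be left off. But n alone would not supply a valid change measure for T and Z scores.

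Some stronger readings are tempting. A reader might infer that these plots are the main display of the endpoint; the SAP introduces them as a supplement to the tables. A reader might infer that patients will leave in country blocks. Availability does depend on country, but the documents give neither site sizes nor the order of exit. A reader might also infer that the earlier study's Z-score gain was an artefact. The last step, −0.478 − (−0.761) = 0.283, is indeed within one SD of chance composition if the 9 are a random subset of the 31: 1.076 × √(1/9 − 1/31) = 0.30. But the whole gain from −1.208 (n=38) is 0.73, beyond the 95% chance band of 1.96 × 1.0546 × √(1/9 − 1/38) = 0.60. The example shows only that a plot of absolute means cannot separate the two explanations.

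**Conclusion.** The point holds for the figures at visits after Week 104. There the absolute-mean line can move with no within-patient change. Under random exit from 32 patients, with a Z-score SD of 0.79 to 1.08, the 95% chance shift is about ±0.27 to 0.37 with 16 left and ±0.47 to 0.65 with 8 left. That exceeds the 0.188 step reported between two visits of an earlier study. Whether it will happen, how far and in which direction cannot be told from the documents.

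For BMD in g/cm² the percent-change plot largely removes the problem. For T and Z scores neither planned figure gives a usable within-patient picture. This does not put the two-year result in doubt, and the tables remain sound. The undefined *total BMD* is a separate labelling gap in the same sentence.

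**What to change.** In SAP 2.4.4.1.3:

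- Name the sites for every figure (lumbar spine, left hip, right hip) in place of *total BMD*.
- For T and Z scores, plot mean absolute change from baseline in patients with both values, and drop the percent-change plots.
- For BMD in g/cm², plot absolute or percent change from baseline in patients with both values.
- Print n under each visit.
- Wherever an absolute mean is plotted, show the baseline mean of the same patients beside it.

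Even mean change comes from different patients at different visits, so n and the matched baseline mean are still needed to read the late points. The cost is SAP wording and minor programming. No new data are required, and the change quantities are already being computed for the tables.

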#### **2.4.4.1.4 Lytic lesions, osteonecrosis, fractures and infarcts**

Total incidence of new or worsening lytic lesions, new or worsening AVN, new or worsening infarctions and new fractures among all locations will be summarized since study entry until all the patients completed their 2-year follow-up period and at end of study. Summary statistics (N, mean, standard deviation, median, minimum and maximum) will be displayed by visit. Annual incidence rates and will also be calculated as total number of incidence divided by the total number of person-years. MRI and X-ray assessment result will be summarized separately.

#### **2.4.4.1.5 Bone biomarkers**

Absolute values, change and percent change from baseline (study baseline and eliglustat baseline) for levels of P1NP, CTx and MIP 1  $\beta$  will be summarized by visit.

#### **2.4.4.2 Analyses of secondary efficacy endpoints**

For secondary analysis blood levels of biomarkers of GD1 (chitotriosidase, GL-1 and lyso-GL-1), for all patients and separately for CYP2D6 URM patients will be evaluated at baseline (study baseline and eliglustat baseline) by visits. Measured values as well as absolute and percent changes from study baseline and eliglustat baseline will be summarized. Analysis similar to those described in [Section 2.4.4.1](#) will be conducted and reproduced.

For lyso-GL-1, analyses will include all available data.

Refer to [Section 2.1.3.2.1](#) for details on how chitotriosidase values will be normalized prior to being used in analyses and for definitions of bone density categories.

#### **2.4.4.3 Multiplicity issues**

Not applicable.

#### **2.4.4.4 Additional efficacy analysis(es)**

Summary statistics (including number, mean, median, standard deviation, minimum and maximum) of the absolute value, change and percentage change from baseline (study baseline and eliglustat baseline) for spleen volume, liver volume, hemoglobin and platelet results will be presented by visit. Descriptive statistics for CYP2D6 URM patients will be analyzed separately.

## 2.4.5 Analyses of safety data

The summary of safety results will be presented for data from the 2-year eliglustat treatment period as well as at study completion by overall. Descriptive summaries will be produced as described below.

### ***General common rules***

All safety analyses will be performed on the safety population as defined in [Section 2.3.2](#), unless otherwise specified, using the following common rules:

- Safety data in patients who do not belong to the safety population (eg, exposed but not included) will be listed separately.
- The study baseline value is defined as the last available value before the first dose of eliglustat of this study. The eliglustat baseline value is defined as the last available value before the first dose of eliglustat of corresponding initial study.
- For quantitative safety parameters based on central laboratory/reading measurements, descriptive statistics will be used to summarize results and change from baseline values by visit and overall group.
- The analysis of the safety variables will be essentially descriptive and no systematic testing is planned.

### ***2.4.5.1 Analyses of adverse events***

#### ***Generalities***

The primary focus of adverse event reporting will be on treatment-emergent adverse events (TEAEs). Pre-treatment adverse events and post-treatment adverse events will be described separately, if applicable.

If an adverse event date/time of onset (occurrence, worsening, or becoming serious) is incomplete, the undetermined adverse event should be treated as treatment-emergent adverse event. Details on classification of adverse events with missing or partial onset dates are provided in [Section 2.5.3](#).

Adverse event incidence tables will present by SOC, HLTG, HLT, and PT, sorted in alphabetical order for overall group, the number (n) and percentage (%) of patients experiencing an adverse event. Multiple occurrences of the same event in the same patient will be counted only once in the tables within a treatment phase. The denominator for computation of percentages is the safety population.

Sorting within tables ensures the same presentation for the set of all adverse events within the observation period (pre-treatment and treatment-emergent). For that purpose, the table of all treatment-emergent adverse events presented by SOC and PT sorted by the internationally agreed SOC order and decreasing frequency of PTs within SOCs will define the presentation order for all other tables unless otherwise specified. Sorting will be based on results for the overall group.

### ***Analysis of all pre-treatment adverse events***

- Overview of pre-treatment adverse events, summarizing number (%) of patients with any
  - Adverse event
  - Serious adverse event
  - Adverse event with special interest (AESI)
  - Adverse event leading to death
  - Severe adverse event

By-patient listing of all pre-treatment adverse event

### ***Analysis of all treatment-emergent adverse events***

The following treatment-emergent adverse event summaries will be generated for the safety population.

- Overview of treatment-emergent adverse events, summarizing number (%) of patients with any
  - Treatment-emergent adverse event
  - Treatment-emergent serious adverse event
  - Treatment-emergent adverse event of special interest (AESI)
  - Treatment-emergent adverse event leading to death
  - Treatment-emergent adverse event leading to permanent treatment discontinuation
  - Treatment-related treatment-emergent adverse event
  - Severe treatment-emergent adverse event
- All treatment-emergent adverse event by primary SOC, HLT, HLT, and PT, showing number (%) of patients with at least 1 treatment-emergent adverse event sorted by the SOC internationally agreed order. The other levels (HLGT, HLT, PT) will be presented in alphabetical order
- All treatment-emergent adverse events by primary SOC and PT, showing the number (%) of patients with at least 1 treatment-emergent adverse event, sorted by the internationally agreed SOC order and by decreasing incidence of PTs within each SOC. This sorting order will be applied to all other tables, unless otherwise specified
- All treatment-emergent adverse events regardless of relationship and related by primary SOC and PT, showing the number (%) of patients with at least 1 treatment-emergent adverse event, sorted by the internationally agreed SOC order and by decreasing incidence of PTs within each SOC
- All treatment-emergent adverse events by maximal severity, presented by primary SOC and PT, showing the number (%) of patients with at least 1 treatment-emergent adverse event by severity (ie, mild, moderate, or severe), sorted by the sorting order defined above

- By-patient listing of all treatment-emergent adverse events
- By-patient listing of all severe treatment-emergent adverse event

